Statistical Analysis Plan

Collaborative Care to Reduce Depression and Increase Cancer Screening among Low-Income Urban Women

NCT Number: 02273206

Document Date: July 30, 2017

**Collaborative Care to Reduce Depression and Increase Cancer
Screening among Low-Income Urban Women – Prevention Care Manager 3 Project**

Statistical Analysis Plan

Overview

The primary analysis was based upon the intention-to-treat (ITT) approach, with data from each participant analyzed as per initial assignment to one of the two intervention arms. Our analysis proceeded in several steps: 1) data checking to identify and resolve the reasons for missing values, inconsistencies, and out-of-range values; 2) descriptive analyses of the baseline characteristics of the two intervention arms; 3) formal comparison of participation in screening tests and changes in depression between the CCI intervention and PCM controls arms, intention-to-treat analyses, per protocol analyses, and analyses that accounted for missing data; and 4) multivariate analyses testing for moderators and mediators.

Data checking and descriptive analysis

Data analysis was preceded by intensive data checking to identify and resolve the reasons for missing values, inconsistencies, and out-of-range values. Summary statistics describing the baseline characteristics of each intervention arm are presented, including age, primary language, marital status, health insurance, smoking status, body mass index, medical history, family history and comorbid conditions, etc. Continuous variables were summarized using means and standard deviations, while categorical variables were summarized using proportions with cut points made for median or quartiles as appropriate. A comparison of the distribution of baseline characteristics was made between the two intervention arms. There were no differences between the two groups with respect to their distribution by baseline characteristics. In addition to the baseline characteristics, we tabulated the study endpoints of interest, the extent of dropouts, and protocol violations for each intervention arm separately.

Intention to treat (ITT) analysis

Data from each study subject were analyzed as per initial assignment to the intervention arm. First, completion of cervical cancer screening (Pap test), breast cancer screening (mammogram), and colon cancer screening (HFOBT/FIT, Barium Enema, Sigmoidoscopy or

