To determine whether reducing depression increases the likelihood that low-income women will receive age-appropriate cancer screening (Aim 3), we included improvement in depression (as well as depression remission in a separate model) in the logistic regression models to examine its association with cancer screenings, and also to examine if the difference between the two intervention arms was modified by change in depression; we examined the interaction between improvement in depression and treatment (as well as depression remission and treatment). To determine whether the effectiveness of the CCI intervention varies according to patient characteristics, such as language spoken and, obesity, etc. (Aim 4), we examined each of these variables as possible effect modifiers. However, it is understood that the statistical power for testing an interaction term may be limited in this study; consequently, this aim was treated as exploratory and the results of this study will be used to design a future, more definitive study with interventions identified and targeted to address issues associated with specific subgroups who may experience reduced benefit from the intervention.

Missing Data

Missing data are a common problem in longitudinal studies. In the context of the present study, missing data will occur when, for example, not all the screening outcomes are reported for a given participant, or some of the co-variables (e.g., body mass index) are missing. For the initial approach in the primary analysis of the study, study participants with missing values on either the outcomes or the co-variables were first removed from the study for the evaluation of intervention effects. However, this approach required the assumption of missing completely at random to be true. A violation of this assumption may lead to bias in the estimate of the intervention effect. We first examined the level of missing data by each outcome and each co-variate in the model. If the rate of missing data is small (<5%), the chance that it will bias the result is very low; however, if the rate of missing data is moderate (>10%), sensitivity analysis was used to examine the robustness of the result. For example, if one variable has a moderate level of missing, we conducted a sensitivity analysis which compared those participants with the remaining participants and also included those participants in the analyses by adding a separate missing category.

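### The primary analysis is complete-case by assigned arm and by the SAP's own account needs MCAR; no named method estimates the treatment effect when outcomes are missing

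*SAP*

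**What the plan says.** The SAP Overview states: "The primary analysis was based upon the intention-to-treat (ITT) approach, with data from each participant analyzed as per initial assignment". It also lists "intention-to-treat analyses, per protocol analyses, and analyses that accounted for missing data" among the planned comparisons, without saying what the last of these are. The section on data checking adds that "we tabulated the study endpoints of interest, the extent of dropouts, and protocol violations for each intervention arm separately".

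The Missing Data section then sets the working rule. As the initial approach in the primary analysis, "study participants with missing values on either the outcomes or the co-variables were first removed from the study for the evaluation of intervention effects". It concedes that "this approach required the assumption of missing completely at random to be true" and that the intervention effect may be biased if the assumption fails. It continues:

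- On how missingness is checked: "We first examined the level of missing data by each outcome and each co-variate in the model".
- On low rates, where it sees little danger: "If the rate of missing data is small (<5%), the chance that it will bias the result is very low".
- On higher rates, where it acts: "if the rate of missing data is moderate (>10%), sensitivity analysis was used to examine the robustness of the result".

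The one sensitivity analysis described is an example for a single variable: compare the women lacking it with the rest, then bring them back in under a separate missing category.

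The section on ITT analysis gives the models: chi-square and logistic regression for each screening test, a proportional odds model for the 0–3 count, t-test and linear regression for continuous outcomes, and multinomial regression for outcomes with more than two levels. Protocol section F takes screening from chart review and self-report. PHQ-9 and SCL-20 are questionnaires, and section C places interviews at baseline, 6 and 12 months.

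**The concern.** Analysing women in the arm they were assigned to is only half of what most readers understand by intention-to-treat. The other half is that every randomised woman counts. Once women with a missing value are removed, the comparison is between those who stayed in each arm, and randomisation no longer protects it. If the women who are lost differ from completers in one way under CCI and in another under PCM, the complete-case difference is biased, and the direction cannot be known in advance.

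The SAP recognises this. The difficulty is that its remedy does not reach missing outcomes. The table of dropouts by arm and the check by variable may show that loss is unequal, but no named method would then show how far the treatment effect could move. Depression is a primary outcome in the protocol and is measured only by interview, so it is the outcome most exposed.

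**Working it through.** **The SAP's own figure.** With 356 women per arm and a 10-point difference, power (normal approximation, two-sided 5%) is Φ{[0.10√n − 1.96√(2p̄(1−p̄))] / √(p₀(1−p₀)+p₁(1−p₁))}. The SAP does not give the PCM rate. At an assumed 60% v 70%: (1.887 − 1.96 × 0.6745)/0.6708 = 0.842, so power is 80.0%. The stated figure reproduces. The 356 are women with complete data, so this calculation concerns precision and says nothing about bias.

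**Likely loss.** Protocol section G recruits 800, and the SAP has 712 with complete data. 1 − 712/800 = 11.0%. Reading this gap as expected loss is an inference. If correct, it lies above the SAP's 10% trigger. Protocol section H reports retention of at least 80% in the sites' earlier trials, so 20% is used as a second value.

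**What the described method can do.**

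1. *Missing covariate.* A missing category keeps the woman in an adjusted model with her observed outcome. It works.
2. *Missing yes/no outcome.* A third level cannot enter a test of two binomial proportions or a binary logistic model. It can enter a chi-square for several categories or a multinomial model, but that tests whether missingness differs by arm. It does not estimate the effect on screening among all randomised women.
3. *Missing continuous outcome.* A t-test or linear regression has no place for a missing category.
4. *Comparing women with and without the value.* This is descriptive and gives no treatment effect.

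**Size for depression scales (illustration).** In each arm the mean over all women is C + f(M − C), with C the completers' mean, M the mean of missing women and f the proportion missing. With equal f in both arms, the complete-case difference is off by f × g, where g is the between-arm difference in (M − C). The documents give no g; 0.25 and 0.5 SD are assumed.

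| Loss f | g = 0.25 SD | g = 0.5 SD |
|---|---|---|
| 11% | 0.0275 SD | 0.055 SD |
| 20% | 0.05 SD | 0.10 SD |

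**Size for screening (illustration).** Assume completers at about 60% (CCI) v 50% (PCM), 400 randomised per arm, missing PCM women at 50%, and a pooled two-proportion z test. Missing outcomes are filled in once, without imputation variance.

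| | 11% loss (44 per arm) | 20% loss (80 per arm) |
|---|---|---|
| Completers | 214/356 v 178/356, z = 2.71, p = 0.007 | 192/320 v 160/320, z = 2.54, p = 0.011 |
| Last non-significant count of missing CCI women up to date | 13 of 44: 227/400 v 200/400, z = 1.914, p = 0.056 | 35 of 80: 227/400 v 200/400, z = 1.914, p = 0.056 |
| One more up to date | 228/400 v 200/400, z = 1.985, p = 0.047 | 228/400 v 200/400, z = 1.985, p = 0.047 |
| All missing counted as not screened | 214/400 v 178/400, z = 2.546, p = 0.011 | 192/400 v 160/400, z = 2.279, p = 0.023 |

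Losing significance needs missing CCI women at 13/44 = 30% or below (11% loss) or 35/80 = 44% or below (20% loss), against 60% in CCI completers.

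**Unequal loss (illustration).** If the true rate is 50% in both arms, all missing women are unscreened, and 5% are missing in one arm and 15% in the other, the observed rates are 0.50/0.95 = 52.6% and 0.50/0.85 = 58.8%. That is a spurious 6.2 points, against the SAP's smallest difference of interest of 10.

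**The case against.** The SAP is not silent on missing outcomes. It checks every outcome, sets a trigger, offers its method only as an example without excluding outcomes, and lists analyses that account for missing data. A reader might infer that it has no provision at all, and that goes too far. What stands is narrower: no named provision yields a treatment effect for a missing binary or continuous outcome.

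A reader might also infer that a check by variable overlooks missingness building up in the 0–3 screening count, which needs three results. The documents do not support this. The SAP names the count as an outcome and checks each outcome, so its own missing rate would be compared with the trigger.

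Deleting women for missing covariates is probably a minor harm. On a model-by-model reading the unadjusted tests are untouched, the SAP reports no baseline differences between arms, and above 10% it already uses a missing category. Below that level the deletion is still unnecessary.

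The SAP does not name the time point of the depression comparison, so one cannot say that a 12-month test discards 6-month data. It remains true that no use of the repeated interviews is stated for women with a missing value.

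Finally, every size above rests on assumed inputs. That is correct, and the conclusion is limited accordingly.

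**Conclusion.** The point holds in this limited form and should be fixed. The primary analysis is complete-case by assigned arm and depends on MCAR. Both facts come from the SAP's own text and are not in doubt. The plan may reveal differential loss, but the only method it describes cannot estimate the effect among all randomised women when a binary or continuous outcome is missing, and it gives no rule for 5–10%.

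The size is unknown. Under the assumed inputs, depression scales could be off by about 0.03–0.10 SD in either direction with equal loss. The screening illustration is not shown to be fragile: with all missing women counted as not screened, significance is kept at both levels of loss. If chart review covers nearly all randomised women, the effect on screening is small or nil. A reader might conclude that the trial's result is biased. The documents give neither a missingness rate nor results by arm, so that cannot be said.

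**What to change.** 1. Run each unadjusted test on every woman who has that outcome. In adjusted models keep women with a missing baseline covariate, at any missingness rate, by simple imputation or the SAP's own missing category.
2. For PHQ-9, SCL-20 and other repeated scales, fit a mixed model to the 6- and 12-month values already collected. For screening, first apply the chart data already held by one rule in both arms, stating how a woman with no record is classified. Then use multiple imputation by arm for what is still missing. State that both methods assume missing at random (MAR).
3. Add a tipping-point analysis whenever outcome missingness is 5% or more or differs by arm. This also closes the 5–10% gap.
4. Report missing outcomes by arm. Keep the present result as a sensitivity analysis, labelled complete-case by assigned arm.

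The SAP is written in the past tense, so label the additions post hoc and report both sets of results.

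The cost is modest reanalysis and revised wording, with no new patients, visits or chart abstraction. MAR cannot be tested either, which is why the tipping-point analysis is needed.

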The PCM intervention components, to be delivered to women randomized to the comparison arm, are a subset of the CCI intervention components, since the new CCI intervention is a combination of PCM cancer screening care management and TCM depression care management. In Figure 2 below, we outline the components of the interventions to be delivered by the care managers in the two study arms, based on the three previous randomized controlled trials of PCM in CHCs conducted by the CDN Team^{76,77,109} and on collaborative care.^{97,99,110,111} A 12-month intervention period was chosen based on the depression collaborative care literature.^{42,96,99,112} PCM was shown to have an effect on cancer screening in eight months.⁷⁷

Figure 2. Intervention Content

	Prevention Care Manager (PCM)	Collaborative Care Model (CCI)
Cancer Screening	
 Educate and increase awareness Provide patient navigation Provide motivational support to overcome barriers to cancer screening 	
 Educate and increase awareness Provide patient navigation Provide motivational support to overcome barriers to cancer screening
Mental Health		
 Provide depression care and motivational support (supportive counseling) Be an interface between primary care and mental health providers Provide linkage to social services

Care Managers and Intervention Delivery

The care managers, performing the functions presented in Table 1, will be female bi-lingual college graduates with a social work or health education background, by education or job experience. A number of studies have found that professionals who are not clinically licensed can serve as effective depression care managers, and this reduces the cost and increases feasibility of dissemination and sustainability,^{97,110} and more resembles the CHC workforce. There will be two half-time care managers in each CHC, one for the CCI. Based on our discussions with our study sites, we expect that most if not all

care managers will be existing staff who are familiar with the health center culture, providers, and systems, including the electronic medical record and referral sources. For both study arms, the intervention is designed to be deliverable by phone, for efficiency in time and cost;¹¹³⁻¹¹⁵ however, we anticipate that enrolled patients may want to meet with the care manager in person as well, especially when at the health center for an appointment.

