Eligible women will be invited to participate in the study. When recruitment is conducted in person, the care manager will make every effort to complete the consent process at that time, and she will also attempt to complete the 45-minute baseline structured interview, described below. If this is not possible, the care manager will schedule another appointment, as soon as possible, to conduct the baseline interview by phone or in person at the CHC. Based on prior collaborative care research with minority patients in these Bronx CHCs and other similar settings, we expect a consent rate of about 70%.^{76,99} In keeping with PCM and other collaborative care research,^{76,112} we will use a randomized block algorithm, stratified by CHC to assign women to the PCM control arm or the CCI intervention arm. Block size will be allowed to vary randomly to preclude any exercise of judgement, or bias, in the allocation of participants to specific arms. Study participants will be randomized 1:1 to each of the two arms, according to a scheme prepared by the study statistician, who is not onsite at any of the CHCs. Randomization will occur after the baseline interview; women in the study will be notified of their assignment at the time of the first call with the care manager. [name], study data coordinator, will disclose the block randomization process and will inform care managers of the assignments. [name], Project Director, will supervise [name] and all aspects of data collection described below.

Initial phone contact

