The care managers will be assigned to the CCI intervention group or the PCM comparison condition prior to training. The care managers assigned to the comparison condition will not be trained on depression care management (the second part of the training) during the active study, to further avoid the possibility of contamination across the groups. They will, however, receive training about what to do when a woman is in acute distress and/or is suicidal. The first part of the training, which will be attended by all care managers, will last eight to ten hours over two days. Care managers will be expected to review all study materials prior to the training. PCM Training will be based on the NIH RTIPS for the Dartmouth-CDN Prevention Care Management Project¹²⁴ and will be conducted by [name], the study Project Director, who has conducted PCM training across multiple studies of care management in cancer screening and PTSD in the past 10 years, with support from the study clinical psychologist. [name], PI for the previous PCM RCTs and the developer of both the PCM and CCI Interventions is a member of the research team and provides training and oversight to the Care Managers. Guided by PCM,⁷⁶ care managers will receive an overview of current screening guidelines of the U.S. Preventive Services Task Force; a review of barriers to breast, cervical, and colorectal cancer screenings; and detailed explanations of the screenings themselves. They will role play in the training about how to elicit barriers from women and how to provide motivational support to help women overcome them. Standard scripts will be provided to support the care managers and facilitate uniformity delivery, and they will need to pass a competency test.

The second part of the manual-based training, which will last ten hours over two days, will be didactic and interactive; it will be led by the project psychologist, with support from [name]. Only care managers assigned to the CCI intervention will participate in this training; as with the first training, they will be expected to review materials beforehand. The focus will be on depression care management and will entail a review of what depression is, including key symptoms, as well as a brief overview of anxiety, which is likely to present in approximately 50% of the depressed women.¹²¹ Guided by the work of Ell and colleagues^{95,99} care managers will also learn about barriers to help-seeking for mental health

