Colonoscopy) were compared separately between the two intervention arms using a chi square test comparing two independent binomial proportions (Aim 1). Next, logistic regression was used to control for potential confounders, including the factors discussed that were identified as being unevenly distributed between the CCI and PCM intervention arms at baseline. To account for possible differences by site, site indicators were included in the model as a fixed effect to examine if there were potential confounders; if they were not found to be confounders, they were removed from the model. A combined ordinal cancer screening outcome, calculated as number of up to date cancer screening tests (which vary from 0 to 3) was analyzed using the proportional odds model (PROC GENMOD in SAS). Other key patient-reported outcomes, including changes in depression, self-efficacy, stigma, satisfaction with cancer screening decision and satisfaction with care, and quality of life, were also compared between the two intervention arms (Aim 2). For continuous outcomes, a two-sample t-test was used to examine the difference between the two arms, and a linear regression model was used to control for potential confounders; for categorical outcomes, a chi-square test was used to examine the difference between the two arms and a logistic regression (for binary outcome) or a multinomial logistic regression (for a categorical outcome with more than two levels) was also used to control for potential confounders.

Multivariate analyses testing for moderators and mediators

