Heterogeneity of Treatment Effects (HTE) Analysis

A potential problem in intervention studies is heterogeneity within the participant population. To examine whether the effectiveness of intervention varies according to patient characteristics, here we focused on BMI and primary language as previous evidence supported that these two characteristics affected the likelihood of being up to date with cancer screening. In addition, because women who were up to date at baseline may be very different from women who were not up to date at baseline, we examined the subset of women who were not up to date for each specific cancer screening and examined if the intervention improved their up to date screening status.

Sample size/Power Calculation

The primary aim of the study was to compare the effectiveness of the Collaborative Care Intervention (CCI) versus Prevention Care Management (PCM) to increase participation in screenings for cervical cancer, breast cancer and colon cancer among women with depression. Women were equally randomized to the two intervention arms. With 356 women in each arm, the study had about 80% power to detect a minimum 10% difference between two arms in cancer screening participation with a two-sided type I error rate of 5%, under various assumptions of screening rate for the PCM (control) group. This 10% difference is considered the smallest difference of interest, based on previous studies comparing the PCM to Usual Care.^{1, 2,3} Therefore, with 356 women with complete data per intervention arm (n=712) our study had sufficient power to detect a clinically meaningful difference between the two intervention arms.

Multiple Comparisons

We evaluated three separate screening outcomes (for cervical cancer, breast cancer and colorectal cancer) so that multiple hypothesis testing would be involved. However, the relative importance of factors contributing to participation in each screening test varied between tests, and we were interested in comparing the two intervention arms for each test separately, as well as globally for all three tests. We also examined a summary of cancer

screening outcome across three types of cancers by comparing the total number of up to date cancer screenings at the follow-up between the two treatment arms, using a regression model for ordinal outcome. Since these statistical tests were hypothesis-driven rather than exploratory, we did not think multiple comparison adjustment for type I error rate was necessary.

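### The screening chi-square and the power figure make no allowance for care managers who each serve one arm only; the power figure also omits the control rates it assumes

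*SAP*

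**What the plan says.** **Power.** The SAP (Sample size/Power Calculation) says "With 356 women in each arm, the study had about 80% power to detect a minimum 10% difference between two arms", at a two-sided 5% level, "under various assumptions of screening rate for the PCM (control) group". None of those rates is listed. The section concludes that "with 356 women with complete data per intervention arm (n=712) our study had sufficient power".

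**Test.** The SAP (Intention to treat (ITT) analysis) compares each screening outcome "using a chi square test comparing two independent binomial proportions". A logistic model follows with site indicators; "if they were not found to be confounders, they were removed from the model". Neither document mentions a care-manager term, an ICC, a design effect or a cluster-robust method.

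**Delivery.** Protocol section B (Care Managers and Intervention Delivery) says "There will be two half-time care managers in each CHC, one for the CCI". Section C (Care Manager Training) adds that "The care managers will be assigned to the CCI intervention group or the PCM comparison condition prior to training", and section C (Subsequent phone contact and activities) describes separate care managers for the two conditions. Women, by contrast, are randomized individually, by a "randomized block algorithm, stratified by CHC to assign women to the PCM control arm or the CCI intervention arm".

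**The concern.** The care manager is the person who delivers the intervention. If some are more effective than others, women on the same caseload have correlated outcomes. Because each caseload lies wholly within one arm, differences between care managers feed directly into the difference between arms.

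The chi-square's standard error contains only binomial variation. With a handful of care managers per arm, a significant result could reflect a few effective individuals rather than the added depression component. The power figure rests on the same independence assumption and on control rates that the reader cannot see, so the claim of adequate power is made without its conditions.

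**Working it through.** **1. Reproducing the stated power.** Inputs from the SAP: n = 356 per arm, 1:1, two-sided 5%, difference d = 0.10. With PCM rate p, CCI rate q = p + 0.10 and mean rate r:

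power = Φ{ (d − 1.96·√[2r(1−r)/n]) / √[(p(1−p) + q(1−q))/n] }

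- p = 0.30: (0.10 − 1.96 × 0.03575) / 0.03555 = 0.842, giving 80.0%.
- p = 0.45: (0.10 − 1.96 × 0.03748) / 0.03729 = 0.712, giving 76.2%.

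| PCM rate | 20% | 30% | 35% | 40% | 45% | 50% | 55% | 60% | 70% |
|---|---|---|---|---|---|---|---|---|---|
| Power | 87.0% | 80.0% | 77.9% | 76.6% | 76.2% | 76.6% | 77.9% | 80.0% | 87.0% |

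The stated figure reproduces at 30% and 60%. The largest shortfall is 80.0 − 76.2 = 3.8 points. At 356 per arm and PCM rates of 35–55%, 80% power corresponds to a difference of about 10.3–10.5 points rather than 10.0.

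**2. Care-manager clustering.** Two care managers per centre (Protocol B) at six centres (Protocol G) imply about 12 in all, six per arm, with m = 356/6 = 59.3 women each. This count is inferred. The ICC (care-manager variance beyond site) is assumed, because the documents give none.

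Design effect DE = 1 + (m − 1)·ICC. True size of the nominal 5% test = 2·[1 − Φ(1.96/√DE)]. For ICC 0.005: DE = 1 + 58.3 × 0.005 = 1.292; 1.96/√1.292 = 1.72; size 8.5%. Power of a test held at a true 5% uses n/DE in the formula above.

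| Assumed ICC | DE | True size | Power at a true 5%, PCM 30–60% |
|---|---|---|---|
| 0 | 1.000 | 5.0% | 76–80% |
| 0.001 | 1.058 | 5.7% | 74–78% |
| 0.005 | 1.292 | 8.5% | 65–69% |
| 0.01 | 1.583 | 11.9% | 56–60% |

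For scale, an ICC of 0.005 at a 45% rate means that care managers' true rates have a standard deviation of √(0.005 × 0.45 × 0.55) = 0.035, or 3.5 points.

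**3. Whether site handling removes it.** In a simulation with six sites, one care manager per arm per site, 59–60 women each and both arms at 45%, the chi-square size was:

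| Total ICC | All care-manager | Half site | All site |
|---|---|---|---|
| 0.005 | 8.3% | 6.7% | 5.0% |
| 0.01 | 11.9% | 8.5% | 4.8% |

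Correlation shared by both arms at a site therefore does no harm, as expected with randomization stratified by site. A site-stratified Mantel-Haenszel test gave 8.3% and 12.0% when all the variance lay between care managers, so stratifying by site does not help.

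**4. What a care-manager analysis can deliver.** With site kept as fixed effects, 12 care managers − 6 sites − 1 arm term leaves 5 degrees of freedom (critical value 2.57). At ICC 0 the noncentrality is 0.10/0.03555 = 2.81 at a PCM rate of 30% or 60%, and 0.10/0.03729 = 2.68 at 45%. Power is then 61.8% and 57.9%.

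**The case against.** **The power figure is not an arithmetic error.** A reader might infer one from the values below 80%. The documents do not support that: the figure reproduces at 30% and 60%, the SAP says it is approximate and depends on the PCM rate, and power exceeds 80% outside that range. What stands is a reporting gap.

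**The test is not shown to be invalid.** A reader might also infer that the chi-square certainly rejects too often. Women are individually randomized. If the question is whether the arms differed as delivered by these particular care managers, an effective care manager is part of what was delivered and the test holds its size. The excess applies only when care managers are treated as a sample and the conclusion is carried to others. The documents do not say which target is meant.

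**The size is uncertain in both directions.** Scripts in both arms, common screening training with a competency test, fidelity review and monthly case meetings (Protocol C) may keep the ICC small; at 0.001 the size is only 5.7%. The number of care managers is also unsettled. Protocol F and I still refer to three health centers, while section K describes one site as a network whose Bronx clinics all take part. At ICC 0.005, three care managers per arm give a size of 12.0%, six give 8.5% and ten give 7.0%.

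**Requiring both analyses to agree would be too strict.** With a true 10-point effect and no clustering at all, a paired-by-site test on 5 degrees of freedom fails to confirm 26–27% of the results that the chi-square finds significant.

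These objections limit the claim, but none supplies the missing allowance or shows that the independence assumption was examined.

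**Conclusion.** The point holds as one about the analysis and the power statement. The documents place each care manager in one arm, and neither the primary test nor the power figure allows for it. Keeping the site indicators in the model, rather than dropping them, would not change this.

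On the view that care managers are a sample of possible deliverers, the true size is about 5.0–11.9% for assumed ICCs of 0 to 0.01 with six equal caseloads per arm. Those figures are illustrations of sensitivity, not estimates for this trial. The unlisted control rates are a minor matter, costing at most 3.8 points of power. Overall this is a change that should be made. Confidence is moderate, because the ICC is assumed and the care-manager count is inferred.

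**What to change.** 1. **Keep the chi-square as the primary test.** The SAP is in the past tense and already reports the baseline comparison, so the primary analysis should not change now.
2. **Add one sensitivity analysis for each screening outcome** that accounts for care manager, by a random intercept or by cluster-robust errors with a small-sample correction, with site kept in the model. Report the estimate and interval, the care-manager ICC with its interval, and the caseloads. If outcomes have already been analyzed, say that it was added afterwards.
3. **Present it descriptively.** Do not make agreement between the two analyses a condition for accepting a result.
4. **State as a limitation** that the primary result assumes no care-manager clustering, and say whether conclusions are meant for these care managers or for others too.
5. **Minor:** list the assumed PCM rates and replace the single power figure with power by PCM rate (20/30/40/45/50/60/70%: 87.0/80.0/76.6/76.2/76.6/80.0/87.0%). Note that this assumes no care-manager clustering, and qualify the conclusion that power was sufficient.

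**Cost:** SAP wording, one table and one added analysis, with no extra patients. The stated power becomes slightly less favourable. The sensitivity intervals will be wider and often inconclusive, with about 58–62% power on 5 degrees of freedom even at ICC 0, and an ICC from about 12 care managers will be imprecise. The analysis also depends on recovering each woman's care manager from the electronic contact database. Protocol C (Care Management Monitoring and Process Evaluation) does not list that identifier among the recorded items, so its availability should be confirmed first.
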